#### 7.5.2 Primary Efficacy Endpoints

Analyses in this section will be performed by treatment group as randomized.

## 7.5.2.1 Primary Analyses

Overall survival and PFS as assessed by BICR in All PD-L1 expressing subjects will be compared between N+I vs CT and between N+C vs CT using a two-sided log rank test, stratified by the stratification factors as specified in Section 7.1.1, i.e. by

- region (J/K/T vs rest of Asia vs RoW),
- ECOG performance status (0 vs. 1),
- number of organs with metastases ( $\leq 1 \text{ vs.} \geq 2$ ).

For each comparison, the HR with its associated two-sided  $100(1-\alpha)\%$  CIs will be estimated via a stratified Cox model with treatment arm as the only covariate in the model.

Overall survival and PFS for each treatment arm will be estimated and plotted using the KM product-limit method. Median survival time along with 95% CI will be constructed based on a log-log transformed CI for the survival function.

Status of Censored Subjects

The status of subjects who are censored in the OS KM analysis will be tabulated for each randomized treatment group using following categories:

- On-study (on-treatment in follow-up);
- Off-study (lost to follow-up, withdraw consent, never treated etc.).

The status of subjects who are censored in the PFS KM analysis will be tabulated for each randomized treatment group using the following categories:

- 1) Censored on randomization date
  - a) no baseline scan
  - b) no on-study scan and no death (or death with prior subsequent therapy)
- 2) Censored on date of last tumor scan on-study
  - a) Received subsequent anti-cancer therapy
  - b) Still on treatment
  - c) In follow-up

- d) Off study
  - i) lost to follow-up
  - ii) subject withdrew consent
  - iii) other

The source of PFS event (death vs. PD) will be summarized by treatment group.

## 7.5.2.2 Sensitivity Analyses

#### • Overall Survival and Progression-Free Survival

- Stratified analysis using stratification factors as obtained from the baseline CRF pages (instead of IRT) except for the number of organs with metastases at baseline which will be retrieved from IRT. This analysis will be performed only if at least one stratification factor at randomization (as per IRT) and baseline are not concordant for at least 10% of All PD-L1 expressing subjects.
  - region (J/K/T vs rest of Asia vs. RoW) from CRF
  - ECOG performance status (0 vs. 1) from CRF
  - number of organs with metastases (≤ 1 vs. ≥ 2) from IRT
- Analysis using a 2-sided, un-stratified log-rank test, an un-stratified Cox proportional hazards model with treatment as the single covariate.
- Analysis for subjects with no relevant deviation. This analysis will be conducted only if there are more than 10% subjects with relevant protocol deviations.

Each of the above analysis will use the same significance level as the corresponding primary analysis. Estimate of the HR, its two sided CI (adjusted as for the corresponding primary analysis) and p-value will be presented.

- A multivariate adjusted, stratified (by factors as specified in Section 7.1.1) Cox model will be fitted to assess the treatment effect when adjusted for potential prognostic factors. The following potential prognostic factors will be included in the model. The list of covariates considered in the multivariate cox model may be modified if there are issues with multicollinearity among the covariates or other important prognostic factors are identified.
  - Age categorization ( $< 65 \text{ vs.} \ge 65$ )
  - Gender (Male vs. Female)
  - Race (Asian vs. non-Asian)
  - Weight ( $< 60 \text{kg vs.} \ge 60 \text{kg}$ )
  - Disease status at current diagnosis (recurrent vs. de novo metastatic and unresectable advanced vs. de novo metastatic)
  - Smoking status (current/former vs. never/unknown)
  - Alcohol use (current/former vs. never/unknown)

For the multivariate analysis, HR and 95% CI will be provided for treatment variable and all covariates. Descriptive p-values will be provided.

• Analysis for investigating non-proportionality in Kaplan-Meier curves. If the Kaplan-Meier curves indicate the HR is not constant over time such as a clear delayed separation, the power of the standard logrank test is reduced. In this case, as suggested by the non-proportional hazards working group, the Max-Combo test is a promising approach with the flexibility of allowing different types of non-proportionality and robustness under model mis-specification. The R package nphsim can facilitate such testing procedures. We will apply the Max-Combo test to the PFS/OS data with the following parameter setting (rho, gamma) of Fleming-Harrington class of weights: (rho = 0, gamma = 0) attributes equal weights to all; (rho = 1, gamma = 0) emphasizes early difference in survival curves; (rho = 0, gamma = 1) weight more for late difference; (rho = 1, gamma = 1) emphasizes middle difference. In the current implementation of the R package nphsim, stratification is not available. Therefore, the unstratified Max-Combo test in the package will be applied and the resulting p-value will be reported, along with estimated HR and adjusted 95% CI. Since the stratification is not involved, the results of this sensitivity analysis should only be compared with the original results of the unstratified analysis.

## Sensitivity analyses for PFS to investigate alternative censoring schemes

- Analysis accounting for assessment on/after subsequent therapy: PFS will be defined similarly to the primary definition except that events (progression or death) and disease assessments that occurred on or after subsequent anti-cancer therapy will be considered (no time point truncation). This definition is considered as primary definition by EMA. The PFS accounting for subsequent therapy (primary definition, Section 4.1.2) is the primary endpoint of the study and will be the basis of the primary test to determine statistical significance.
- PFS accounting for two or more consecutively missing disease assessments prior to PFS event: This analysis will be performed only if at least 10% of PFS events have missing prior disease assessments. In case a subject has two or more consecutively missing disease assessments, the subject will be censored at the last disease assessment date prior the PFS event.
- Analysis in which progression-free subjects who are lost to follow-up for any cause will be considered as having an event at the time of the last tumor assessment date prior to loss to follow-up.

Each of the above analysis will use the same significance level as the corresponding primary analysis. Estimate of the HR, its two sided  $100(1-\alpha)\%$  CI and p-value will be presented.

## 7.5.2.3 Consistency of Treatment Effect in Subsets

To assess consistency of treatment effects in different subsets, a "forest" plot of the OS and PFS unstratified HR (and 95% CI) will be produced for the following subgroups.

- Age category ( $< 65, \ge 65 \text{ and } < 75, \ge 75, \ge 65$ )
- Gender (male, female)
- Race (Asian, non-Asian)
- Region (J/K/T, Rest of Asia, RoW) (*stratification factor*)

- Region (Asia, Non-Asia)
- ECOG PS (stratification factor)
- Weight ( $< 60 \text{kg}, \ge 60 \text{kg}$ )
- Disease stage at initial diagnosis (Stage I, Stage II, Stage III, Stage IV)
- Histologic grade at initial diagnosis (Gx, G1, G2, G3, G4, Not Otherwise specified)
- Histological classification at initial diagnosis (squamous cell carcinoma, adenosquamous cell carcinoma, other)
- Location at initial diagnosis (upper thoracic, middle thoracic, lower thoracic, gastroesophageal junction)
- Disease status at current diagnosis (recurrent loco-regional, recurrent distant, de-novo metastatic, unresectable advanced)
- Smoking status (current/former, never/unknown)
- Alcohol use (current/former, never/unknown)
- Number of organs with metastases at baseline ( $\leq 1 \text{ vs.} \geq 2$ ) (stratification factor)
- Time from Initial Disease Diagnosis to Randomization (< 1 year, 1 < 3 year, 3 -< 5 year, ≥ 5 year)

- Prior surgery (excluding biopsy) (Yes or No)
- Prior radiotherapy (Yes or No)

If subset category has less than 10 subjects per treatment group, HR will not be computed/displayed. Number of events and median OS/PFS along with 95% CI will be displayed for each treatment group.

For the purposes of the subset analyses, stratification factors will be retrieved from the CRF except for the number of organs with metastases at baseline which will be retrieved from IRT.

## 7.5.2.4 Subjects follow-up

The extent of follow-up is defined as the time between randomization date and last known date alive (for subjects who are alive) or death date (for subjects who died) will be summarized descriptively for all subjects randomized.

The currentness of follow-up for OS is defined as the time between last OS contact (i.e., last known date alive or death date) and data cut-off date. Subjects who died and subjects with last known alive date after data cut-off date will be considered as current for this analysis.

The currentness of follow-up for PFS is defined as the time between last tumor assessment date (regardless of initiation of subsequent therapy) and cut-off date. Subjects who have a PFS event (regardless of initiation of subsequent therapy) and subjects with last tumor assessment date on or after data cut-off will be considered as current for this analysis.

The currentness of follow-up for OS and PFS will be summarized by treatment group, and will be categorized in categories.

#### 7.5.2.5 Survival Rates

Overall survival and PFS rates at 6, 12, 18, 24, 36, 48 months and at 5 year will also be estimated using KM estimates on the OS and PFS curves for each randomized arm. Minimum follow-up must be approximately longer than or equal to timepoint to generate the rate. Associated two-sided 95% CIs will be calculated using the Greenwood's formula.

## 7.5.3 Secondary Efficacy Endpoints

Secondary endpoints are: OS and PFS by BICR in All Randomized Subjects, ORR by BICR in All PD-L1 expressing subjects and in All Randomized subjects.

Analyses for each of these endpoints will be performed by treatment group as randomized.

## 7.5.3.1 Overall Survival and PFS by BICR in All Randomized Subjects

As specified by Figure 7.5.1-1, if any of the primary endpoints is significantly superior, the corresponding secondary endpoint in all randomized subjects will be compared using a two-sided log rank test at the allocated significance level, stratified by the stratification factors as specified in Section 7.1.1. (I.e. by the same stratification factors as the primary endpoints plus by PD-L1 status  $[\ge 1\% \text{ vs.} < 1\%]$  as recorded in IRT.)

For each comparison, the HR with its associated two-sided 95% CI (in case the given endpoint is formally tested, also with the  $100(1-\alpha)\%$  CI) will be estimated via a stratified Cox model with treatment arm as the only covariate in the model. OS and PFS for each treatment arm will be estimated and plotted using the KM product-limit method. Median survival time along with 95% CI will be constructed based on a log-log transformed CI for the survival function. 

#### Additional Analyses for OS and PFS in All Randomized Subjects

The same additional analyses will be carried out for OS and PFS in All randomized Subjects as for OS and PFS in All PD-L1 expressing subjects, i.e.:

- Status of censored subjects (Section 7.5.2.1)
- All sensitivity analyses (Section 7.5.2.2)
- Analyses by subsets (Section 7.5.2.3)
- Extent of follow-up and currentness of follow-up (Section 7.5.2.4)
- Survival rates (Section 7.5.2.5)

#### 7.5.3.2 Objective Response Rate by BICR

All analyses in this section will be carried out for All PD-L1 expressing subjects and for All Randomized subjects as well.

Best Overall Response will be summarized by response category for each treatment group.

**ORR** (as assessed by BICR) in subjects with PD-L1 expressing tumors and in all randomized subjects will be tested only if significance level is passed on them. For rules for passing on

significance levels, see Section 7.5.1. Comparisons will use a two-sided CMH test (as detailed in Section 7.1.1).

ORR will be computed in each treatment group along with the exact 95% CI using Clopper-Pearson method. An estimate of the difference in ORRs and corresponding 95% CI (in case the given endpoint is formally tested, also with the  $100(1-\alpha)\%$  CI) will be calculated using CMH methodology and adjusted by the stratification factors as specified in Section 7.1.1. The stratified (source: IRT) odds ratios (Mantel-Haenszel estimator) between the treatments will be provided along with the 95% CI (in case the given endpoint is formally tested, also with the  $100(1-\alpha)\%$  CI).

For additional analysis related to ORR by BICR, see Section 7.5.4.3.

## 7.5.4 Exploratory Efficacy Endpoints

Analyses in this section will be performed in all randomized subjects and in All PD-L1 expressing subjects, by treatment group as randomized.

## 7.5.4.1 Progression-Free Survival by Investigator

Hazard ratio (N+C vs CT and N+I vs CT) with its associated two-sided 95% CI will be estimated via a stratified Cox model with treatment arm as the only covariate in the model. PFS for each treatment arm will be estimated and plotted using the KM product-limit method. Median survival time along with 95% CI will be constructed based on a log-log transformed CI for the survival function. 8,9

The PFS rates, the source of PFS event (death vs. PD), and the status of subjects who are censored in the PFS KM analysis will be evaluated the same way as for PFS by BICR.

#### 7.5.4.2 PFS2/TSST

Hazard ratio (N+C vs CT; N+I vs CT) with its associated two-sided 95% CI will be estimated via a stratified Cox model with treatment arm as the only covariate in the model. PFS2/TSST for each treatment arm will be estimated and plotted using the KM product-limit method. Median PFS2/TSST time along with 95% CI will be constructed based on a log-log transformed CI for the survival function. 8,9

The PFS2/TSST rates and the source of PFS2/TSST event (death vs. PD vs. second next line systemic therapy) will be evaluated.

## 7.5.4.3 Endpoints Related to Best Overall Response

Duration of Response and Duration of SD (as assessed by BICR and by investigator) in each treatment group will be estimated using KM product-limit method for subjects who achieve PR or CR. Median values along with two-sided 95% CI will be calculated.

For DOR, type of event (PD, death) and status of subjects censored (received subsequent therapy, ongoing follow-up [current, non-current], off study [withdrew consent] will be presented by treatment arm.

Time to objective response (TTR as assessed by BICR and by investigator): summary statistics will be provided for each treatment group for subjects who achieve PR or CR. Cumulative Response Rates will be tabulated for Week 6, Week 12, Month 4, 6, 8, and 12, and overall Response Rate will be provided for each treatment group.

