### **Exploratory Endpoints**

Progression free survival, PFS2/TSST, and ORR as assessed by investigator (in subjects with PD-L1 expressing tumors and in all randomized subjects) will be described using the same methods as the corresponding secondary endpoints.

Duration of Response (as assessed by BICR and as assessed by investigator) in each treatment group will be estimated using KM product-limit method for subjects who achieve PR or CR. Median values along with two-sided 95% CI will be calculated.

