## 4.2.3 Objective Response Rate per BICR in All Randomized Subjects

Objective response rate as assessed by BICR in subjects with PD-L1 expressing tumors and in All Randomized subjects are secondary endpoints for this study.

It is defined as the number of subjects with a best overall response (BOR) of CR or PR divided by the number of randomized subjects in the population for each treatment group. BOR is defined as the best response designation as determined by BICR per RECIST 1.1, recorded between the date of randomization and the date of objectively documented progression or the date of subsequent anti-cancer therapy (including tumor-directed radiotherapy and tumor-directed surgery), whichever occurs first. For subjects without documented progression or subsequent anti-cancer therapy, all available response designations will contribute to the BOR determination. For subjects who continue treatment beyond progression, the BOR will be determined based on response designations recorded up to the time of the initial RECIST 1.1-defined progression.

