## **Duration of Response**

Duration of Response (as assessed by BICR and as assessed by investigator) is defined as the time between the date of first documented response (CR or PR) to the date of the first disease progression, per RECIST 1.1 or death due to any cause, whichever occurs first. For subjects who neither progress nor die, the duration of objective response will be censored at the same time they were censored for the primary definition of PFS. DOR will be evaluated only for subjects whose BOR is CR or PR.

Survival rate, PFS rate and duration of Stable Disease (SD) are not positioned as objectives per protocol, but will be evaluated.

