# **Duration of Stable Disease**

Duration of SD is defined as the time between the randomization date and the date of the first documented tumor progression (per RECIST 1.1) or death due to any cause, whichever occurs first. Censoring rules will be the same as for DOR analysis. It will be evaluated only for subjects whose BOR is SD.

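### SAP 7.5.4.3 and SAP 4.3.1 give contradictory populations for duration of stable disease: responders in the one, subjects whose best response is SD in the other

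*SAP*

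**What the plan says.** SAP 4.3.1 defines the two endpoints separately and gives each its own population.

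- **DOR** runs from first documented response to progression or death. On the population: "DOR will be evaluated only for subjects whose BOR is CR or PR".
- **Duration of SD** has a different starting point: "Duration of SD is defined as the time between the randomization date and the date of the first documented tumor progression", or death from any cause. On the population: "It will be evaluated only for subjects whose BOR is SD".

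The same section states the standing of the second endpoint: "Survival rate, PFS rate and duration of Stable Disease (SD) are not positioned as objectives per protocol, but will be evaluated".

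SAP 7.5.4.3, which gives the analysis, joins the two. Its opening sentence has as its subject "Duration of Response and Duration of SD", by BICR and by investigator, and says that these "will be estimated using KM product-limit method for subjects who achieve PR or CR". Medians with two-sided 95% confidence intervals follow. The introduction to SAP 7.5.4 applies this to all randomized subjects and to all PD-L1 expressing subjects, by arm as randomized.

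The matching sentence in Protocol 8.4.2, under Exploratory Endpoints, has the same restriction to responders but a narrower subject: "Duration of Response (as assessed by BICR and as assessed by investigator) in each treatment group will be estimated using KM product-limit method". It does not mention duration of SD.

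**The concern.** One endpoint has two populations in the same document. The endpoint section assigns duration of SD to subjects whose best response is stable disease; the analysis section assigns it to responders. Someone programming from 7.5.4.3 and someone programming from 4.3.1 would select different subjects and produce different tables under the same title.

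Taken literally, 7.5.4.3 also produces a quantity that does not match its name. The clock for duration of SD starts at randomization and stops at progression or death. Applied to responders, that is a PFS-type time in the responding subset, reported as duration of stable disease.

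The output is meant to be reported. SAP 4.3.1 commits to evaluating it, and SAP Section 11 sends the analyses described in the SAP to the clinical study report unless noted otherwise.

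**Working it through.** The point involves no sample size, power, alpha or event count, and the plan gives no figure to reproduce. The check is a comparison of text.

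**Step 1. The populations side by side.**

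| Endpoint | SAP 4.3.1 | SAP 7.5.4.3 | Protocol 8.4.2 |
|---|---|---|---|
| DOR | BOR of CR or PR | PR or CR achieved | PR or CR achieved |
| Duration of SD | BOR of SD | PR or CR achieved | not mentioned |

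The DOR row agrees throughout. The SAP disagrees with itself only in the second row.

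**Step 2. Does anything else in 7.5.4.3 supply an SD population?** No. The remaining text covers event type and censoring status for DOR, and time to response in subjects with PR or CR. Nothing there qualifies the opening sentence for SD.

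**Step 3. Do the two populations overlap?** SAP 4.2.3 says: "BOR is defined as the best response designation as determined by BICR per RECIST 1.1". This is a single best designation per subject, and the investigator version in 4.3.1 is defined by analogy. For a given assessor, the set with BOR of SD and the set with BOR of CR or PR are therefore disjoint. On that reading, 7.5.4.3 includes none of the subjects that 4.3.1 calls for.

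One qualification applies. Section 7.5.4.3 speaks of achieving PR or CR, not of BOR. Protocol Appendix 5 requires confirmation of response, and its Table 4.2-1 gives a subject with PR followed by SD a best response of SD. If an unconfirmed response counted as achieving PR, such subjects would fall in both sets. The title of 7.5.4.3 refers to best overall response, which favours the BOR reading and hence no overlap.

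**Step 4. What does each reading estimate?**

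- Under 4.3.1: randomization to progression or death, in subjects whose best response is SD.
- Under 7.5.4.3 as written: randomization to progression or death, in responders.

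**Step 5. How many outputs are involved?** Two assessors (BICR, investigator) × two populations (all randomized, PD-L1 expressing) × three arms = 2 × 2 × 3 = 12 distinct Kaplan-Meier estimates with medians. All are descriptive.

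**Step 6. Likely origin.** The sentence in Protocol 8.4.2 covers DOR alone, and for DOR the restriction is correct. The SAP sentence has the same form with duration of SD added to its subject. This suggests an addition made without adjusting the end of the sentence, though the documents do not prove it.

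**The case against.** The strongest reply is that the SAP already contains the right answer. Section 4.3.1 is the endpoint definition, and its restriction to BOR of SD is explicit and exclusive. It also gives DOR its own matching rule. A programmer who starts from the definition would select the right subjects. This stands: a reader of 7.5.4.3 alone might infer that the sponsor has planned the analysis in the wrong subjects, but the documents do not support that. They show two sections in conflict, and do not settle which would be followed. SAP Section 11 also refers to a Data Presentation Plan with table mock-ups, which is not among the documents reviewed and may settle the population at output level.

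A second reply is that almost nothing depends on the result. Duration of SD is not a protocol objective and is absent from the overview of major efficacy endpoints in SAP Table 4-1. SAP 7.1.1 confines type I error control to primary and secondary endpoints. Section 7.5.4.3 plans medians and intervals, with no test between arms. This also stands and sets the ceiling on importance.

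Two further inferences are tempting, and neither is supported.

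- A reader might conclude that the reported figure would overstate disease control. Longer progression-free time in responders is plausible, but neither document compares responders with SD subjects on this measure, and the SAP plans no disease control rate for this trial. Direction and size remain unquantified.
- A reader might size the problem from the response table in Protocol 1.1.3. Those counts come from a single-arm nivolumab monotherapy study in patients refractory or intolerant to standard therapy. They say nothing about how many subjects will have SD or a response in a first-line, three-arm combination trial.

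None of these replies removes the contradiction. No other sentence in either document repairs 7.5.4.3.

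**Conclusion.** The point holds as an internal contradiction on the population for duration of SD. The sentence in 7.5.4.3 is correct for DOR and wrong for duration of SD when set against 4.3.1. Followed literally, it would label a responder time-to-progression-or-death estimate as duration of stable disease and would exclude the subjects required by the definition. That the two sets are fully disjoint assumes that achieving PR or CR means a BOR of PR or CR.

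The importance is low. The consequence is confined to descriptive, exploratory output that carries no alpha. No primary or secondary analysis, test or conclusion changes. It looks like a drafting slip rather than a methodological choice, but it is worth correcting because the analysis section is what output is built from.

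**What to change.** Split the opening sentence of SAP 7.5.4.3 into two, for example:

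- DOR, by BICR and by investigator, is estimated by Kaplan-Meier in each arm among subjects with BOR of CR or PR.
- Duration of SD, by BICR and by investigator, is estimated by Kaplan-Meier in each arm among subjects with BOR of SD.

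Take BOR from the same assessor as the duration being estimated. Using BOR in both sentences also removes the doubt about unconfirmed responses. If the mock-ups in the Data Presentation Plan show a different population, align them.

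The cost is one sentence in the SAP. Both populations already stand in SAP 4.3.1, so no design decision is needed, and no test, alpha level or data collection changes.
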